## Protocol Summary

Title of Study:	Reduction of Hip Arthroscopy Post-operative Pain Using Ultrasound-guided Fascia-iliaca Block
Study Type:	Postmarket
Primary Investigator:	[name]
Primary Endpoint:	Quantify the difference in pain in patients who have received a pre-operative Fl block versus those receiving no block
Secondary & Tertiary Endpoints:	
 
Secondary endpoint: Quantify the difference in opioid consumption in patients who have received a pre-operative Fl block versus those receiving no block (local anesthetic/Noropin (30cc of 0.5%) joint injection only).
 
Tertiary endpoints: Assess differences in episodes of PONV, time in PACU, and proportion of unplanned admissions
 

Design:	Prospective, randomized, two-arm, single-blind study
Length of Study:	3M follow-up
Sample Size:	95 subjects

## Schedule of Events

	BL	Proc	2W	6W	3M
Informed Consent	✓	-	-	-	-
Inclusion/Exclusion	✓	-	-	-	-
Surgical Details	-	✓	-	-	-
Physical Exam-ROM	✓	-	✓	✓	✓
Visual Analogue Scale (VAS)	✓	-	✓	✓	✓
Adverse Event Assessment	-	✓	✓	✓	✓

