## Study Methodology

- Study Description

- Design: Randomized controlled trial
- Blinding:
  - Blinded: Data analyst
  - Unblinded: patient, surgeon and anesthesiologist
- Location: Greenville Health System (Patewood Outpatient Hospital and Hillcrest Memorial Hospital)
- Sample size: Sample size estimates are based on the assumptions of a large clinical effect size (>.40) seen at 5 follow up points for the primary outcome measure of pain. Using a fixed effects, special, main and interactions, analysis of variance testing (ANOVA) with a power of 0.80 and an alpha of 0.05, we estimate the need for 86 subjects to achieve statistical significance. To account for loss of follow up, we will target 10% more subjects, thus 95 total participants.
- **Study population**
  - Subjects
    - Recruitment: Consecutive patients undergoing hip arthroscopy will be enrolled in the study
    - Inclusion criteria:
      - Scheduled for outpatient hip arthroscopy by [name]
      - ASA 1-3
      - Ages 18-65
    - Exclusion criteria:
      - Prior surgery on ipsilateral hip
      - ASA 4-6
      - Chronic narcotic usage over 6 months or more than the equivalent of 20mg of morphine per day
      - Current or prior placement of a spinal cord stimulator or intrathecal pump for pain control purposes
      - Allergy to amide local anesthetics
      - Contraindication to regional anesthesia
      - BMI > 40
      - Females who are pregnant or plan to get pregnant during the course of the study

- **Study procedure**

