The study incorporates four dedicated follow up points beyond baseline: a) perioperative (1 to 5 days), b) 2 weeks, c) 6 weeks, and d) 3 months. The primary outcome measure (pain) will be analyzed using a fixed effects, special, main and interactions, analysis of variance testing (ANOVA). Opioid consumption will be analyzed using a Pearson chi square or parametric equivalent (depending on final coding). Tertiary end points will be captured using an ANOVA for continuous measures (once tests of normality are completed), or Kruskal Wallis, whereas re-admission rates will be analyzed using a Pearson Chi-square. A p value of 0.05 will be considered statistically significant for all findings. Intention to treat and last value carried forward will be integrated for all analyses.

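### Baseline VAS is scheduled but is not a covariate in the primary pain ANOVA: a free gain in precision is left unused, though the randomised comparison is not biased

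*Combined protocol and SAP*

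**What the plan says.** - **Schedule of Events.** The row "Visual Analogue Scale (VAS" is ticked at baseline, 2 weeks, 6 weeks and 3 months. It is not ticked at the procedure.
- **Statistical Analysis.** "The primary outcome measure (pain) will be analyzed using a fixed effects, special, main and interactions, analysis of variance testing (ANOVA". The section names no covariate and no change score, and gives baseline pain no other role. On timing it says: "The study incorporates four dedicated follow up points beyond baseline", and then lists a perioperative point, 2 weeks, 6 weeks and 3 months.
- **Study Methodology, sample size.** The calculation uses the same ANOVA and assumes a "large clinical effect size (>.40) seen at 5 follow up points for the primary outcome measure of pain". It continues "with a power of 0.80 and an alpha of 0.05, we estimate the need for 86 subjects" and, for loss to follow-up, "we will target 10% more subjects, thus 95 total participants".
- **Protocol Summary.** The design is a "Prospective, randomized, two-arm, single-blind study". No allocation ratio is given.

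**The concern.** Pain is the primary outcome and is to be measured before treatment, yet the analysis never says how that measurement is used. Two things follow.

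First, if pre-operative pain predicts post-operative pain, a model without it carries between-patient variation that could be removed at almost no cost. It also leaves any chance difference between the arms at baseline uncorrected. With 43 per arm the standard error of the baseline difference is √(2/43) = 0.22 SD, so a visible imbalance would not be unusual.

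Second, the role of baseline in the time factor is undefined. The sample-size text counts five follow-up points and the analysis text counts four after baseline. Four plus baseline makes five, so one possible reading is that baseline is a level of time. Baseline precedes treatment and carries no expected arm difference, so averaging it into an arm main effect would pull that effect towards zero.

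**Working it through.** **The plan's own figure.** Read .40 as Cohen's f, with alpha 0.05, power 0.80 and noncentrality f²N. A fixed-effects F test with 5 numerator degrees of freedom then needs N = 86 with 2 to 6 groups (87 with 8 to 12). The plan does not state the numerator df; 1 df would give 52 and 4 df would give 80. Adding 10%: 86 × 1.10 = 94.6, hence 95. The stated size therefore reproduces, and the calculation contains no baseline covariate.

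**Inputs for the check**
- 43 per arm: 86/2, assuming 1:1 allocation.
- Standardised difference d, two values. d = 0.61 is an assumption, chosen because it gives about 80% power at 43 per arm; it is not in the documents. d = 2f = 2 × 0.40 = 0.8 is the plan's figure read as Cohen's f for two equal arms.
- Correlation r between baseline and follow-up VAS: not in the documents, so a range is shown.

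**Single time point.** Adjusting for baseline multiplies the residual variance by 1 − r², so the effective difference becomes d/√(1 − r²). For example, at r = 0.5, 0.61/√0.75 = 0.704. Power is from a two-sided two-sample t test at 0.05.

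| r | Variance reduction (r²) | Power, d = 0.61 | Power, d = 0.8 |
|---|---|---|---|
| no covariate | – | 0.798 | 0.956 |
| 0.1 | 1% | 0.802 | 0.958 |
| 0.3 | 9% | 0.834 | 0.970 |
| 0.5 | 25% | 0.898 | 0.989 |
| 0.7 | 49% | 0.975 | 0.999 |

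Estimating the covariate slope costs about 1% of variance (83/82 = 1.012 at N = 86), which the table ignores. The break-even correlation is √(1 − 82/83) = 0.11. At r = 0.1 there is in effect neither gain nor loss.

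**Several time points.** Suppose four post-operative scores are averaged, with a common correlation ρ between all scores, baseline included. The variance of the mean is (1 + 3ρ)/4, and adjustment subtracts ρ². The ratios of adjusted to unadjusted variance are:
- ρ = 0.1: 0.315/0.325 = 0.97
- ρ = 0.3: 0.385/0.475 = 0.81
- ρ = 0.5: 0.375/0.625 = 0.60
- ρ = 0.7: 0.285/0.775 = 0.37

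Under this assumption the single-time-point table does not overstate the relative gain.

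**Baseline as a level of time (conditional).** Suppose the effect is d at every post-operative point and 0 at baseline. The arm main effect averaged over all levels is (0 + 4d)/5 = 0.8d with the four points of the Statistical Analysis section. It is (0 + 3d)/4 = 0.75d with the three post-operative VAS visits in the Schedule of Events. This applies only if baseline is a level and the arm main effect is the test.

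**The case against.** The strongest case against has four parts.

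1. *Nothing is invalid.* The unadjusted post-operative comparison is unbiased under randomisation, and 86 is correct on its own inputs. This stands: the point is about efficiency and clarity only.

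2. *The gain may be small.* The block is aimed first at immediate post-operative pain, and pain reported at a pre-operative clinic visit may predict recovery-room pain weakly. If .40 is Cohen's f, power is already 0.956 and adjustment adds at most about 4 percentage points. This also stands, and no particular gain can be promised. However, three of the four analysis points are clinic visits from 2 weeks to 3 months, so the case does not rest on recovery-room scores alone.

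3. *Dilution is not in the plan.* A reader might infer from the five-versus-four mismatch that baseline is a level of time and that the treatment effect is therefore diluted. The documents do not support that. Nowhere is baseline called a level. The fifth point could equally be the recovery-room scores, and a change-from-baseline analysis is neither stated nor excluded. Even if baseline were a level, only the arm main effect would shrink. In the arm-by-time interaction, baseline acts as the reference and the effect is spread over several degrees of freedom, not shrunk. The plan includes both kinds of term and does not say which is the primary test.

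4. *Baseline can legitimately sit among the outcomes.* A constrained longitudinal model does this, with one baseline mean common to both arms. That is correct, and the fix allows it.

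**Conclusion.** The point holds as a loss of precision. The primary pain model omits a baseline measurement that the schedule already collects. At one time point the loss is r² of the residual variance, from 1% at r = 0.1 to 49% at r = 0.7. In power, that is 0 to 18 percentage points if d = 0.61 and 0 to 4 if d = 0.8. These figures rest on 1:1 allocation with 43 per arm, on assumed values of r, and on two values of d of which only the second derives from the plan.

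The ambiguity over five or four follow-up points is real and should be resolved. Shrinkage to 4/5 or 3/4 is what would follow from one unstated reading combined with one unstated choice of test; it is not a finding about the plan as written. Neither bias nor an incorrect sample size follows from this point.

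**What to change.** In the Statistical Analysis section, state that the primary pain model includes baseline VAS as a covariate and uses only post-operative scores as outcomes. A constrained longitudinal model with a common baseline mean would serve the same purpose. Reconcile the five follow-up points in the sample-size text with the four in the analysis text, and say explicitly that baseline is not an ordinary level of time with its own arm effect. The covariate does not settle which time point or model term is the primary test; that needs stating too, and the same sentence is the natural place.

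Cost: a sentence or two in the plan and one model degree of freedom. No extra visits, data or patients are needed. Making the change before outcome data are examined also removes a later choice between ignoring, adjusting for and averaging in baseline. Label: free improvement.

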## Abbreviations and Acronyms

FI = fascia iliaca

US = ultrasound

PONV = post-operative nausea and vomiting

PDNV = post-discharge nausea and vomiting

PACU = post-anesthesia care unit

## Introduction / Background

Hip arthroscopy can be a very painful procedure causing patients distress in the immediate post-operative period and beyond. As more and more procedures are planned on an outpatient basis, the pain associated with hip arthroscopy can result in unplanned admission of a patient who expected to be discharged home after their procedure. Currently, opioids are the mainstay of treatment for pain control after hip arthroscopy. Various adjuncts have been tried in the past including multimodal analgesia, hip joint injections, and peripheral nerve blocks typically involving the lumbar plexus and the femoral nerve. Studies of blocks of the lumbar plexus using the posterior approach have shown good results with reduction in patients' pain scores and opioid consumption. However, because of the invasiveness and possible complications of the posterior approach to the lumbar plexus, the anterior approach called the fascia iliaca (FI) block is an attractive alternative. Furthermore, earlier studies of the FI block were performed without benefit of visual guidance for needle insertion. With the advent of ultrasound guidance, the FI block may be placed with a greater degree of success than in previous years when ultrasound guidance was not utilized during the placement of FI block. The aim of the present study is to determine if ultrasound guided FI blocks can reduce the pain scores and opioid consumption of hip arthroscopy compared to an opioid-only regimen using a randomized controlled trial comparing these outcomes in patients getting preoperatively placed FI blocks versus patients not receiving a block. A significant improvement in pain control and opioid consumption in FI patients compared to controls could provide a basis for increased utilization of FI blocks for this procedure with the attendant benefits. Other outcomes assessed include unplanned admission, PONV and PDNV from decreased narcotic usage, and decreased time in the PACU.

- Primary objectives: Quantify the difference in pain score and opioid consumption in patients who have received a pre-operative FI block versus those receiving no block (local anesthetic joint injection only).
  - Secondary objectives: Assess differences in episodes of PONV, time in PACU, and proportion of unplanned admissions compared to patients with joint injection only
- Hypothesis: Pre-operative placement of an ultrasound-guided fascia iliaca block in patients undergoing hip arthroscopy will result in reduced pain scores and opioid consumption compared to patients receiving an opioid-only regimen.
  - Secondary hypothesis: Pre-operative placement of an ultrasound-guided fascia iliaca block in patients undergoing hip arthroscopy will result in fewer episodes of PONV, reduced time in PACU, and lower rates of unplanned admissions compared to patients receiving an opioid-only regimen.

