Patients will be followed in the study surgeon's clinic office per his standard protocol at 2 weeks, 6 weeks, and 3 months post-operatively. Pain scores will be evaluated at this time. Clinical outcome measures and range of motion of the patients' hips will be collected at this time as well. Any adverse reaction from the block will be noted and recorded at all times from the administration of the block and at each clinic follow up. Any signs or symptoms of numbness in the distribution of the fascia iliaca block will be noted.

- Primary endpoint: Quantify the difference in pain in patients who have received a pre-operative FI block versus those receiving no block.
  - Secondary endpoint: Quantify the difference in opioid consumption in patients who have received a pre-operative FI block versus those receiving no block.
  - Tertiary endpoints: Assess differences in episodes of PONV, time in PACU, and proportion of unplanned admissions
- Risks / benefit
  - Risks associated with FI blocks are the following:

Overall the procedure has a very low risk profile. The location of the injection means the risk of intravascular injection, local anaesthetic toxicity, and mechanical nerve damage is extremely low.

Good aseptic technique will minimize the risk of infection. The injection of a large volume of local anaesthetic ensures good spread and reduces the risk of failure. The risk of local anaesthetic toxicity is highest within the first 15 minutes after injection, which makes close monitoring mandatory.
  - The potential benefit is improvement in pain control and opioid consumption in FI patients. The knowledge gained from this study will also be used in future patients with this condition.

- **Statistical Analysis**

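### Opioid consumption is a primary objective in the Introduction but a secondary endpoint elsewhere, and no success rule settles which outcome carries the primary claim

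*Combined protocol and SAP*

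**What the plan says.** The plan ranks its outcomes in two incompatible ways.

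- **Introduction / Background, objectives:** "Primary objectives: Quantify the difference in pain score and opioid consumption". Pain and opioid consumption are both primary. PONV, PACU time and unplanned admissions are secondary.
- **Introduction / Background, main hypothesis:** the block "will result in reduced pain scores and opioid consumption compared to patients receiving an opioid-only regimen". One hypothesis contains both outcomes, and the secondary hypothesis covers PONV, PACU time and admissions.
- **Protocol Summary:** the primary endpoint is pain only ("Quantify the difference in pain in patients who have received a pre-operative Fl block versus those receiving no block"). Opioid consumption is ranked lower ("Secondary endpoint: Quantify the difference in opioid consumption in patients who have received a pre-operative Fl block"), and PONV, PACU time and admissions are tertiary.
- **Study Methodology, endpoint list:** the same ranking as the Protocol Summary ("Secondary endpoint: Quantify the difference in opioid consumption in patients who have received a pre-operative FI block").
- **Study Methodology, sample size:** sized for pain alone as the primary outcome measure, with alpha 0.05 and power 0.80, giving 86 subjects, or 95 with the allowance for loss to follow-up.
- **Study Methodology, Statistical Analysis:** "The primary outcome measure (pain) will be analyzed using a fixed effects". Opioid consumption has its own separate test. Then: "A p value of 0.05 will be considered statistically significant for all findings".

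No section gives a testing order, a multiplicity adjustment, or a rule saying whether success means pain, either outcome, or both.

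**The concern.** The rank of an outcome decides what the trial may claim and at what error rate. Here the objectives and main hypothesis support one ranking, and the endpoint, sample-size and analysis text supports another. With 0.05 applied to everything and no success rule, a report could cite either part of the protocol. If pain failed and opioid consumption succeeded, the objectives could be quoted to present opioid consumption as a primary result. If pain succeeded and opioid consumption failed, the endpoint list could be quoted to call it secondary. A choice made after the results are known is what a pre-specified hierarchy is meant to prevent.

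The readings also differ in their operating characteristics. One leaves the error rate at its nominal value, one can raise it, and one lowers the power to meet the primary objective. The sample size corresponds only to the first.

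**Working it through.** **Inputs from the protocol.** Alpha 0.05, power 0.80, effect size 0.40, N = 86 and 95 after the allowance (Study Methodology, sample size); two arms (Protocol Summary); 0.05 for all findings (Statistical Analysis).

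**Assumed, because the protocol does not give them.** Two-sided tests; effect size read as Cohen's f; numerator degrees of freedom of the ANOVA; correlation between the pain and opioid test statistics (0 to 0.7, with 0.9 added for the error rate); power of the opioid test.

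**Step 1. Reproduce the stated sample size.** Fixed-effects ANOVA, noncentral F with λ = N·f². With N = 86 and f = 0.40, λ = 86 × 0.16 = 13.76. With 5 numerator degrees of freedom and 2 groups, power is 0.802, and 86 is the smallest N that reaches 0.80. With 10 groups it is 87. The allowance is 86 × 1.10 = 94.6, so 95. The stated figures are reproduced. They concern one outcome, pain, at the full 0.05. The 5 degrees of freedom were inferred from the match.

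**Step 2. Pain is the sole primary.** One primary outcome at 0.05. The conflict over opioid consumption adds nothing to its error rate, and the sizing applies as stated.

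**Step 3. Either outcome may support the primary claim.** If the tests are independent, the chance of at least one false positive is 1 − (1 − 0.05)² = 1 − 0.9025 = 0.0975, which is 0.0975 / 0.05 = 1.95 times nominal. For correlated tests it is 1 minus the bivariate normal probability that both statistics lie within ±1.96:

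| Assumed correlation | False-claim rate | Multiple of 0.05 |
|---|---|---|
| 0 | 0.0975 | 1.95 |
| 0.3 | 0.0951 | 1.90 |
| 0.5 | 0.0907 | 1.81 |
| 0.7 | 0.0835 | 1.67 |
| 0.9 | 0.0704 | 1.41 |

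**Step 4. Both outcomes are required.** A false joint claim needs a false rejection on at least one outcome for which the null is true, so its probability cannot exceed 0.05. No adjustment is needed, but power falls. If each test has 80% power, joint power is 0.80 × 0.80 = 0.64 under independence. By the bivariate normal it is 0.67, 0.69 and 0.71 at correlations 0.3, 0.5 and 0.7. The 80% for opioid consumption is an assumption, so these values are illustrative.

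**Step 5. What an explicit either-outcome rule would cost.** Splitting alpha at 0.025 each gives 1 − 0.975² = 0.0494 under independence. With f = 0.40 and 5 degrees of freedom, N rises from 86 to 101 (101 × 1.10 = 111.1, so 112 with the same allowance). If N stays at 86, power for pain falls from 0.80 to 0.71. The choice of hierarchy is therefore a design decision.

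**The case against.** The strongest reply is that the operative text already names one primary outcome. The Protocol Summary, the sample size, the endpoint list and the Statistical Analysis section all treat pain as primary, and only the objectives and hypothesis statements depart from this. Most of this stands: it shows which way the conflict should be resolved. It does not remove the conflict, because all of these sections are current text, none is said to take precedence, and the objectives and hypothesis are where a reader looks for what the trial set out to show.

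A reader might infer that the trial's chance of a false primary claim is nearly doubled. The documents do not support that. It requires two primary outcomes, a rule that either one suffices, and nearly independent tests. No section states such a rule. The hypothesis joins the outcomes with *and*, and the background likewise speaks of improvement in both as the basis for wider use, so the wording leans towards requiring both, which inflates nothing.

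A reader might also infer that the trial has only 64% power. That is not shown either. The figure needs the both-required reading, independence, and an 80% power for opioid consumption that the protocol never states.

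It is also fair to say that a fixed sequence is one valid remedy among several, and that it cannot operate until the pain test is pinned down. The planned ANOVA covers main effects and interactions without saying which effect decides.

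**Conclusion.** The point holds as an internal contradiction on the primary outcome, with the lower tiers displaced in the same way and no success rule to settle it. The plan is wrong as written here and should be corrected before analysis.

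The consequence depends on the reading: no added error if pain is the sole primary; a false-claim rate of up to 9.8% if either outcome suffices (about 9.5% to 8.4% at assumed correlations of 0.3 to 0.7); or error of at most 5% with joint power of roughly 64% to 71% if both are required, given 80% power for each test and a correlation of 0 to 0.7. The documents do not establish that the error rate is actually inflated. What they establish is that the choice among these readings is still open and could be made with the results in hand.

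**What to change.** 1. **Introduction / Background:** make pain the sole primary objective and the sole content of the main hypothesis, as the sample size already assumes. Make opioid consumption secondary. Make PONV, PACU time and unplanned admissions tertiary in both the objectives and the hypotheses, so that they match the Protocol Summary and the endpoint list.
2. **Statistical Analysis:** name the single effect in the pain ANOVA that decides the primary claim. Test opioid consumption confirmatorily at 0.05 only if that effect is significant, and fix its test in advance, since the method now depends on how the variable is coded. Report tertiary endpoints as exploratory, and replace the blanket 0.05 statement accordingly.

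**Cost.** A wording amendment. The 86/95 sample size and the 0.05 for pain are unchanged. The price is that no confirmatory opioid claim is possible if pain is not significant. Because opioid reduction is part of the stated aim, the sponsor should accept that knowingly. If the sponsor prefers to keep both outcomes primary, the protocol must state whether either or both must succeed. An either-outcome rule needs an alpha split, with the sample-size or power cost shown in Step 5. A both-required rule needs a stated power for opioid consumption.

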At the pre-operative clinic appointment, patients will be recruited into the study. Informed consent will be obtained from the patient by the study doctor. The nature of the experiment will be explained, specifically that the patient agrees to be randomized to receive a block prior to the operation or to receive the joint injection at the conclusion of the surgery as an adjunct to general anesthesia. If the patient agrees to enter into the study, the patient will be randomized by use of a computer generated randomization program at the time of enrollment in the clinic. Currently, the standard of care at the Steadman Hawkins Clinic of the Carolinas is to offer surgical patients a block as an analgesic option. Fl blocks are not ordered by the doctor without a request by the patient. If patients do not receive a Fl block, they will receive a local anesthetic intraoperatively by the surgeon at the close of the procedure, which is also currently the standard of care for hip surgery.

On the day of surgery, all patients will receive multimodal analgesia with an oral preoperative cocktail consisting of acetaminophen 15mg/kg up to a maximum of 1000mg, celebrex 400mg, lyric 75mg, and oxycontin 10mg unless they are allergic to any of the components. Both block (B) and non-block (NB) patients will receive pre-operative midazolam 1-5 mg as needed for procedural sedation (B) or pre-operative anxiety (NB) respectively.

Patients to be blocked will receive not less than 50 ml and up to 60 mL of 0.35% ropivacaine at a dose of 3 mg/kg (with adjuvants of 100 mcg clonidine [per 60 mL] and epinephrine 1:400,000) placed using a 17 gauge 3.2" B-Braun Tuohy needle under ultrasound guidance using a SonoSite S-Nerve machine with a 15-10 MHz 38 mm probe using a caudad to cephalad in-plane approach. (A 70kg patient would receive all 60 mL of the block solution and 210mg of ropivacaine total). The blocks will be placed exclusively by a selected group of anesthesiologists, who have been trained in the technique.

Patients who are randomized to no-block will receive a single injection of Noropin in the joint space.

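### The aim and both hypotheses name an opioid-only comparator that no arm receives; the randomized comparison is block versus joint injection on shared multimodal analgesia

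*Combined protocol and SAP*

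**What the plan says.** The aim, in the Introduction / Background, is to find out whether the block can "reduce the pain scores and opioid consumption of hip arthroscopy compared to an opioid-only regimen". The same sentence then describes the controls simply as patients without a block. The main hypothesis is that the block "will result in reduced pain scores and opioid consumption compared to patients receiving an opioid-only regimen". The secondary hypothesis, on nausea and vomiting, recovery time and admissions, ends in the same way: "compared to patients receiving an opioid-only regimen".

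The objectives in the same section name a different control. The primary objectives compare patients given the block "versus those receiving no block (local anesthetic joint injection only"), and the secondary objectives also use the joint injection as the comparator.

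The study procedure under Study Methodology sets out the treatment. On the day of surgery "all patients will receive multimodal analgesia with an oral preoperative cocktail", whose components include acetaminophen and celebrex as well as oxycontin, with omission allowed for allergy. For the control arm: "Patients who are randomized to no-block will receive a single injection of Noropin in the joint space". The consent description presents randomization as a choice between a block before surgery and a joint injection at its end, either one added to general anesthesia.

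**The concern.** A hypothesis fixes what a result is taken to mean. Read literally, these hypotheses would turn a significant difference into a statement that the block improves on opioids alone, and a null result into a statement that it does not. The design supports neither.

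- A difference from patients who had a joint injection does not estimate the difference from patients who had only opioids.
- A null result against a control that includes local anesthetic does not show that the block fails against opioids alone.

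The Introduction / Background says that a significant improvement could support wider use of the block. The identity of the control therefore decides which practice claim the data can carry.

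**Working it through.** The check is a comparison of sections. No new figure is proposed.

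**Step 1. List every comparator named.**

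| Place | Comparator |
|---|---|
| Introduction / Background, aim | opioid-only, then patients without a block |
| Introduction / Background, primary objectives | no block, with joint injection |
| Introduction / Background, secondary objectives | joint injection |
| Introduction / Background, main hypothesis | opioid-only |
| Introduction / Background, secondary hypothesis | opioid-only |
| Protocol Summary, primary endpoint | no block |
| Protocol Summary, secondary endpoint | no block, with Noropin joint injection |
| Study Methodology, study procedure | joint injection |
| Study Methodology, primary and secondary endpoints | no block |
| Study Methodology, sample size | none named |
| Study Methodology, Statistical Analysis | none named |

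Three descriptions are in use: opioid-only, no block, and joint injection. The second is true but incomplete. The third matches the treatment plan. The first does not.

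**Step 2. Test whether opioid-only could be shorthand.** The Introduction / Background calls opioids the mainstay and lists three kinds of adjunct to them: multimodal analgesia, hip joint injections and peripheral nerve blocks. In those terms the control arm receives opioids plus two of the three (multimodal analgesia and a joint injection). The block arm receives opioids plus multimodal analgesia and a nerve block. Neither is opioid-only in the protocol's own vocabulary.

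**Step 3. Count the patients.** The allergy exception covers only components of the oral mixture. A control patient who omits some of them is still due the joint injection, and allergy to amide local anesthetics is an exclusion criterion. A patient in the other arm is due the block. By plan, the number on an opioid-only regimen is 0 of 95.

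**Step 4. Check whether the sample size depends on the wording.** Inputs from the sample-size paragraph are an effect size of 0.40 (taken here as Cohen's f), alpha 0.05 and power 0.80. The noncentral F calculation uses λ = f² × N and denominator df = N − number of groups. The numerator df is not stated. With 5 it gives N = 86 for 2 to 6 groups, where λ = 0.16 × 86 = 13.76. Then 86 × 1.10 = 94.6, rounded up to 95. Both planned figures reproduce. The calculation contains no term for the comparator's name, so rewording the hypotheses leaves them as they are.

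**The case against.** The strongest reply is that this is a slip of terminology. The real comparator appears in both objectives, in the secondary endpoint of the Protocol Summary, in the consent description and in the treatment description. The aim sentence itself goes on to speak of patients without a block. The Statistical Analysis section is organized by outcome and does not refer to opioid-only controls, so no test or estimate rests on the phrase. The passage on what a positive finding would mean refers simply to controls.

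All of that is correct, and it limits the point to wording. It does not remove the contradiction, because the hypotheses are where the trial states its claim, and they state it about a group that does not exist.

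Four stronger readings are tempting, and the documents do not support them.

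- A reader might infer that the trial cannot answer its question. It can: the randomized comparison of block with joint injection is sound on this point.
- A reader might infer that results are bound to be reported as benefit over opioids alone. No section says so, and the objectives point the other way. The most that can be said is that a result could be misread.
- A reader might infer that the assumed effect was conceived against opioids alone, so that power against the actual control is lower. The sample-size paragraph ties its effect size to no comparator, so this is conjecture.
- A reader might compare the local anesthetic amounts in the two arms to judge how active the control is. They are given at different sites and times, and the block solution has added agents. The documents give no basis for reading a ratio of milligrams as relative pain relief.

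**Conclusion.** Wrong as written, in the aim and both hypotheses. They name a comparator that 0 of 95 patients are planned to receive, and they conflict with the objectives, the secondary endpoint in the Protocol Summary and the study procedure. The fault lies in the statement of the claim. The randomization, the planned analysis and the figures of 86 and 95 are unaffected.

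The conclusion rests on two readings: that the treatment description governs what patients receive, and that the joint injection is the alternative to the block and not care given to both arms, as the consent description presents it.

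**What to change.** In the aim and both hypotheses, replace the opioid-only comparator with the one already in the objectives and study procedure: no block, with an intra-articular local anesthetic injection at the end of surgery, against the protocol's background of multimodal analgesia and general anesthesia in both arms. Referring to the protocol's background keeps the allergy exception and the anesthesiologist's discretion intact, which a promise of identical care would not.

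Use the same comparator wording for the primary endpoint in the Protocol Summary and in Study Methodology. State that conclusions are limited to block versus joint injection in that setting.

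This is a text amendment. Treatment, data collection, analysis and sample size stay as they are. The only cost is that the trial claims less.
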